	
 4) Previous radical treatment to the prostate (radiotherapy or surgery) 5) PSA increase of at least 3 assays in the same laboratory over the last 12 months. 6) 1-5 pelvic lymph node metastases detected with 18FCH-PET. A relapse in the dressing prostatectomy is associated possible. 7) Upper limit of lymph node metastases: aortic bifurcation 8) Respect of dosimetry constraints to organs at risk 9) Treatment with hormone therapy may be started before inclusion, to a maximum of three months prior to Day 1 of radiotherapy. This hormone will necessarily be preceded by a free interval treatment of at least 6 months since the last injection, by adding the duration of action of this predictable injection (1, 3 or 6 months) 10) Patient affiliated to a social security scheme 11) Patient Information and written informed consent form signed
NON-INCLUSION CRITERIA	
 1) Bone or visceral metastatic relapse associated 2) Para-aortic nodal relapse (the upper limit is tolerated aortic bifurcation) 3) More than 5 lymph node metastases 4) Proof of metastases at initial diagnosis 5) Evidence of distant metastases in the pelvic lymph nodes or outside the prostate bed prior pelvic lymph nodes irradiation. Irradiation of the bed of the prostate is not an exclusion criterion, but the junction between prior irradiation bed prostatectomy and radiation field pelvic lymph nodes should be examined carefully 6) Castration resistance defined by clinical or biochemical progression despite a combined androgen blockade 7) Known contraindications to pelvic irradiation (eg, chronic inflammatory bowel disease, ...) 8) Known contraindications to hormone therapy, according to standard recommendations in force 9) Serious hypertension not controlled by appropriate treatment 10) Other concomitant cancer or history of cancer (within 5 years prior to study entry), except basal cell or squamous cell carcinomas of the skin. 11) Patient with a psychological, familial, sociological or geographical potentially hampering compliance with the study protocol and follow-up schedule 12) Patient already included in another interventional study involving the approval of a cpp during his screening for the study Oligopelvis 13) Private person of liberty or major trust

E) INVESTIGATIONAL TREATMENT DESCRIPTION

Experimental procedure

- **Radiation therapy**

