A simultaneous integrated boost will be applied to PTVs. It will be administered 5 days per week during 5 to 7 weeks.

The radiation therapy will start three months (+/- 15 days) after the first injection of IADT.

General recommendations

The use of intensity-modulated radiation therapy (IMRT) is mandatory.

Irradiation will be delivered to patients with an empty rectum. It is recommended that the patient empties his bladder and rectum one hour before the planning CT scan and before each radiotherapy treatment, and then drink at least 1/3 L of water after voiding. The one-hour delay will be adapted to the patient's continence.

If the prostate bed has been previously irradiated, it is recommended that the irradiation be delivered with the bladder empty in order to avoid re-irradiation of the bladder due to overlapping fields.

Daily verification of patient's organ positioning using IGRT is mandatory.

The use of a record and verify processing software is mandatory.

Preparation of treatment

A planning CT of the pelvic cavity that includes all of the pelvic lymph nodes will be performed in the supine position, with intravenous contrast agent to aid visualization of the pelvic vessels. Oral contrast agent will also be administered to assist in the determination of the small bowel volume. The minimum CT resolution will be at least 3 mm thick slices every 3 mm, but thinner slices may be necessary for very small volume lymphadenopathy. Merging the CT with pelvic MRI may help to visualize the vascular axes and pelvic lymph nodes.

Fusion with FCH-PET (or PSMA-PET): The FCH-PET (or PSMA-PET) images will be segmented using a threshold adapted to the size of the lymphadenopathy. These images will be used to locate the pathological lymph nodes, but the tumor volume (GTV) will be contoured on the planning CT.

Target Volumes

a) Metastatic lymph nodes

GTV1 to GTV5 will be delineated on the planning CT-scan with the aid of FCH or PSMA PET.

A margin of 3-5 mm around the GTVs will define the clinical target volumes (CTVs).

An additional margin of 3-5 mm around the CTVs will define the planned target volumes (PTVs). The intersection between PTVs and small intestine will be removed from the PTVs.

b) Whole pelvic lymph node irradiation

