- DVH for intestine, bladder and rectal wall, PTV and CTV that meet dose constraints;
- a statement that patients will be treated with an approved daily image guidance technique.

All treatment plans will be sent via a web-based platform for central review and approval prior to beginning radiotherapy.

Quality control of IMRT: all IMRT plans will undergo quality assurance evaluation with ion chamber measurements or an equivalent method of dose verification to verify the absolute dose for each IMRT field, and film dosimetry to measure the relative dose for each IMRT field, as is standard clinical practice. An independent monitor unit calculation may be substituted for ion chamber dosimetry when available.

Management of previously irradiated patients

When the prostate/prostate bed has been irradiated previously, a cumulative dosimetric study will be performed to assess for radiotherapy volumes overlap, and the 20 Gy isodose will be drawn.

If any PTV1-5 has received more than 20 Gy during a previous course of irradiation, the patient should be excluded from the study.

If less than 20 Gy was delivered to PTV1-5, the lower limit of PLN PTV will be restricted to PTV1-5. No modification of the dose constraints will be applied.

Dose adjustment

No dose adjustments will be made.

- **Hormonotherapy**

Hormone therapy is recommended Eligard 45 mg acting for 6 months.

It will be ideally administered the day of start of radiation therapy or within 3 months before the first day of radiotherapy.

Nevertheless, free prescription is left to investigators.

When using other hormonal strategies (anti-androgen agonists, LHRH antagonists or LHRH), an administration for six months will be critical.

F) STATISTICAL CONSIDERATIONS

SAMPLE SIZE DETERMINATION

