DESCRIPTION OF ANALYSIS SETS	
The statistical analysis will be conducted with SAS 9.4 (Institute Inc., Cary, NC, USA), Stata 13.1 Special Edition (StataCorp LP, College Station, Texas, USA). For all analyses, a p-value of less than 0.05 was considered as statistically significant. All reported p-values are two sided.
 
Description of analysis sets Data from all evaluable patients will be analyzed.
 
Descriptive statistics A descriptive analysis of the patients included will be carried out. This analysis will include point estimates, numbers and percentages for qualitative variables, and mean, standard deviation, median, quantiles and range for quantitative variables.
 
Analysis of safety endpoints If a patient presented the same toxic event several times, only the higher grade event was analyzed.
 
Analysis of survival endpoints The different survival endpoints were analyzed are defined as follows:
 
Progression-free survival (PFS): time from randomization until biochemical-clinical failure or death from any cause. The definition of a biochemical-clinical failure is detailed in section 8.5.1. Overall survival (OS): time from randomization until death from any cause.
 
Patients for whom the event will not occur during the follow-up period will be censored at their last follow-up date. For PFS and OS, the determination of survival curves will be performed by means of Kaplan-Meier method.
 
Analysis of quality of life scoring Quality of life scores were compared between baseline and 6 months, and between baseline and 12 months using a Wilcoxon signed test for matched pairs. A Benjamini-Hochberg procedure was applied to control for false discovery rate. Quality of life differences were considered as clinically relevant when greater than 10.
 
Statistical criteria for stopping the study An analysis of acute toxicity persisting at one month after radiotherapy will be performed after the inclusion of the 20th patient to ensure that the toxicity of the irradiation protocol is not higher than expected. If, among the first 20 patients, 10 or more patients present with grade 2 toxicity, we can state that the rate of grade 2 complications is greater than the reference norm of 30 % ($p = 0.048$). In this case the Data Safety Monitoring Board (DSMB) will meet to analyze the toxicity and decide whether to continue the study. If, among the first 20 patients, 2 or more patients present with grade 3 toxicity, we can state that the rate of grade 3 complications is above the reference norm of 2 %

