
(p = 0.059). In this case the DSMB will meet to analyze the toxicity and decide whether to continue the study.

G) STUDY CALENDAR

DURATION OF INCLUSION PERIOD	24 months
TREATMENT DURATION	ADT + IG-IMRT: 6 months of ADT / 6 to 7 weeks (30 fractions) of IG-IMRT
POST TREATMENT FOLLOW UP	10 years
PRIMARY ENDPOINT ANALYSIS EXPECTED DURATION	2 years
STUDY COMPLETION DURATION (INCLUDING FU PERIOD)	12,5 years

SCHEDULE OF STUDY ASSESSMENTS

Visits	Inclusion Max 2 months prior to RT day 1	Treatment period	follow-up		
			M1 1 month after end of RT	Before progression Every 6 months during 2 years	After progression Every 6 months until death
Inclusion/exclusion criteria	X				
Signed consent form	X				
Inclusion (max 2 months prior to RT)	X				
FCH PET	X (a)				X (b)
Physical examination with PS	X	X (d)	X	X	X
Prior history, tumor characteristics	X				
Blood Pressure	X	X (d)	X	X	
Acute toxicity during ADT and RT (f)		X (d)	X		
Late toxicity (f)				X	
QLQ-C30 et QLQ-PR25	X		X	X	
PSA	X		X (f)	X (f)	X (f)
Testosterone	X (g)		X	X	X
ADT (c) + RT		X			

(a) maximum 3 months prior to initiation of ADT

(b) at progression

(c) 6 months treatment starting on RT day 1 or maximum 3 months prior to RT

(d) once per week during RT

(e) biochemical progression = PSA higher than inclusion PSA with 2 successive rises in the same laboratory

(f) NCI-CTCAE v4.0

(g) 28 days prior to ADT

STUDY DIAGRAM

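### The quality-of-life baseline is tied to inclusion and not to the start of ADT, so change from baseline may understate the hormonal effect in patients already on ADT when they complete the form

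*Combined protocol and SAP*

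**What the plan says.** **When the form is completed.** In section G, Schedule of study assessments, the row "QLQ-C30 et QLQ-PR25" is marked in the inclusion column, headed "Inclusion Max 2 months prior to RT", then at M1 and in the six-monthly follow-up. It has no footnote. In the same column, testosterone carries footnote (g), "28 days prior to ADT", and FCH PET carries footnote (a), which also counts back from the start of ADT.

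**When ADT starts.** Four places address this, and they do not agree:

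- Section E, Radiation therapy: "The radiation therapy will start three months (+/- 15 days) after the first injection of IADT".
- Inclusion criterion 9: "Treatment with hormone therapy may be started before inclusion, to a maximum of three months prior to Day 1 of radiotherapy".
- Section E, Hormonotherapy: "It will be ideally administered the day of start of radiation therapy or within 3 months before the first day of radiotherapy".
- Section G, footnote (c): "6 months treatment starting on RT day 1 or maximum 3 months prior to RT".

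**How the scores are analysed.** Section F, Analysis of quality of life scoring: "Quality of life scores were compared between baseline and 6 months, and between baseline and 12 months". The test is a Wilcoxon test for matched pairs, and differences above 10 points count as clinically relevant. Baseline is not defined in relation to ADT, and no adjustment for time on ADT is planned.

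**The concern.** The treatment under study is RT combined with six months of ADT, in a single arm. With no control group, the patient's own baseline is the only reference for quality of life. If that baseline is taken after ADT has begun, any hormonal effect already present becomes part of the reference and drops out of the change score. If ADT has ended by the later visit, recovery from it can appear as improvement. Both errors make the combined treatment look better tolerated than it was. If some patients complete the form before ADT and others during it, the pooled change averages two different contrasts and is judged against one 10-point threshold.

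**Working it through.** The plan states no sample size, effect size or standard deviation for quality of life, so there is no figure of its own to reproduce. The check is interval arithmetic on the stated windows.

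**Inputs** (1 month = 30 days; using 30.4 days moves results by about 1 day)

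- I = days from inclusion to RT day 1: 0 to 60 (section G).
- L = days from first ADT injection to RT day 1: 90 ± 15, that is 75 to 105 (section E, Radiation therapy); or 0 to 90 (Hormonotherapy and footnote (c)). Criterion 9 sets the same maximum of 90.
- Days on ADT at the baseline form: E = L − I. A negative value means the form precedes ADT.

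**1. Under the Radiation therapy text**

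- Earliest inclusion (I = 60): E = 75 − 60 = 15 to 105 − 60 = 45; nominally 90 − 60 = 30.
- Inclusion just before RT (I = 0): E = 75 to 105.
- With the three-month cap (L at most 90): E = 15 to 30 at the earliest inclusion, and 75 to 90 just before RT.

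E is positive throughout, so no patient treated to this text can have a pre-ADT baseline.

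**2. Under criterion 9, Hormonotherapy and footnote (c) alone**

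| ADT start before RT (L) | E at I = 60 | E at I = 30 | E at I = 0 |
|---|---|---|---|
| 0 days | −60 | −30 | 0 |
| 30 days | −30 | 0 | 30 |
| 60 days | 0 | 30 | 60 |
| 90 days | 30 | 60 | 90 |

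The baseline ranges from 60 days before ADT to 90 days into it. With ADT on RT day 1, every form is completed before ADT or on its first day.

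**3. The follow-up end of the contrast.** A six-month (180-day) course ends 180 − L days after RT day 1. Under the Radiation therapy text that is 180 − 105 = 75 to 180 − 75 = 105 days after RT day 1. Section F does not say where the 6 months are counted from. If from RT day 1, the 6-month form comes 180 − (180 − L) = L days after the course ends, that is 75 to 105 days. If from the baseline form, the gap is L − I, that is 15 to 105 days. On either origin, an on-ADT reference is compared with a score taken after the nominal end of the course.

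**4. What the change score loses.** Let D be the deterioration at a visit relative to a pre-ADT score, and b the part of the hormonal effect already present at the baseline form. The observed deterioration is D − b. If the hormonal effect has fully resolved by that visit and nothing else has changed, D = 0 and the patient shows an improvement of b. The documents give no value for b. It could lie anywhere between zero and the whole hormonal effect. If a share q of patients complete the form on ADT, the average shift is q times the mean of b among them. Under the Radiation therapy text q = 1; under the other three passages q cannot be derived.

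**The case against.** The strongest reply is that the all-patients result rests on one passage out of four. In the case that the hormonotherapy text calls ideal, ADT starts on RT day 1 and no baseline is affected. The 45-day upper figure also needs an ADT lead longer than the three-month maximum in the other passages. Both points stand, so the conclusion is conditional and both ranges are given.

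A reader might go further and infer that change from baseline hides the hormonal part of the effect altogether. The documents do not support that: only b is lost, effects that develop after the form still show, and nothing in the plan says how much of the effect is present after 15 to 45 days. Nor do they support calling the pooled change uninterpretable. The test is paired, so each patient remains his own reference; mixing baselines alters what the average means without emptying it. An example in which a 10-point drop is entirely present at baseline would simply assume its own answer.

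Two further points have some force. The quality-of-life objective names only its instruments, so reading it as the effect of RT plus ADT is an inference, though a natural one given the treatment under study. And PET and testosterone may come from tests done before inclusion, whereas a study questionnaire generally needs enrolment first. The two footnotes therefore show that the plan anchors some baseline measures to ADT; they do not show that the form could be moved without other changes.

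**Conclusion.** The concern holds in conditional form. The baseline form is anchored to inclusion and not to ADT. It falls at least about 15 days into ADT for every patient if the Radiation therapy text governs, and for an unknown share of patients if the other passages do. In those patients the 6- and 12-month changes may understate the hormonal effect, and recovery may read as improvement. The timing result follows from the stated windows and needs only the 30-day month. The direction of the bias assumes that ADT worsens at least some domains and that some of this is present at the baseline form. Its size cannot be calculated from the documents. Quality of life is secondary objective (g), with no decision rule attached. The primary design (39 of 63 evaluable patients) is unaffected. This should be corrected, but it does not threaten the trial's main conclusion.

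**What to change.** 1. Reconcile the ADT-to-RT interval in section E (Radiation therapy and Hormonotherapy), criterion 9 and footnote (c) with each other and with the two-month inclusion window. Which timing stands is for the sponsor to decide.
2. Have the baseline QLQ-C30 and QLQ-PR25 completed before the first injection whenever the patient is enrolled before ADT starts.
3. Record days on ADT at the baseline form for every patient.
4. In section F, define baseline relative to the first injection and report change separately for pre-ADT and on-ADT baselines. Describe on-ADT results as change from an on-ADT reference, not as the effect of the full RT plus ADT treatment.

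**Cost.** Items 3 and 4 need no new form or visit. They can also be applied to data already collected, provided that the dates of the first injection and of the form were captured. Item 2 is more than a footnote if the Radiation therapy interval is kept: a pre-ADT form would then fall at least 75 to 105 days before RT, which is 15 to 45 days outside the 60-day window. The window would have to change or an earlier contact be added, so some patients would be enrolled earlier. Separate reporting gives smaller groups in a study of 70, and the pre-ADT group could be very small or empty if most patients start ADT before enrolment.

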	
two consecutive increases measured in the same laboratory; and/or
 
 An increase in the number of metastatic sites on follow-up imaging assessments. 	
SECONDARY OBJECTIVES AND ENDPOINTS		
Secondary objectives	Endpoints	Evaluation time
a) Biochemical relapse-free survival	
A PSA > 0.2 ng/mL after the post-treatment nadir (or PSA > nadir + 0.2 ng/mL if nadir > 0.2 ng/mL).
 
For patients without a history of prostatectomy, biochemical recurrence is defined by:
 
 A PSA > pre-treatment nadir AND A PSA > 0.2 ng/mL after the post-treatment nadir 	2 years
b) Time to resumption of hormone therapy	Resumption of hormone therapy	5 years
c) Time to initiation of any subsequent treatment	Resumption of any treatment	5 years
d) Assessment of toxicity (acute toxicity assessed 1 month after the end of radiotherapy, and late toxicity assessed at 2 years), with particular attention to gastrointestinal events	NCI-CTC-AE v4.0 scale	5 years
e) Site of relapse: within the irradiated field or at distant (non-irradiated) sites	
At least one morphological imaging (depending on recurrence location and center practice):
 
 Abdominopelvic CT scan and/or Pelvic MRI and/or Bone scintigraphy and/or FCH-PET (post-treatment PET will be optional). 	5 years
f) Overall survival	Overall survival	5 years
g) Quality of life	QLQ-C30 + QLQ-PR25	5 years
h) Optional ancillary biological study: validation of a novel mutational signature in patients with oligometastatic prostate cancer treated with radiotherapy		
INCLUSION CRITERIA	
 Histologically proven adenocarcinoma of the prostate Patients aged 18 years or more PS 0-1 	

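### The visit table ends scheduled follow-up of progression-free patients at 2 years, which conflicts with the 5-year evaluation times and the stated 10-year follow-up; if the table governs, 5-year censoring is informative

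*Combined protocol and SAP*

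**What the plan says.** Three parts of the plan describe how long patients are followed.

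- **Section G, schedule of assessments.** After the visit one month after radiotherapy there are two follow-up columns: "Before progression Every 6 months during 2 years" and "After progression Every 6 months until death". No column covers a patient who is still progression-free after year 2. Late toxicity is ticked only in the first of the two columns.
- **Section G, study calendar.** The line "POST TREATMENT FOLLOW UP" gives 10 years, with no split by progression status. The total study duration is 12.5 years.
- **Section C, secondary objectives.** The evaluation time is 5 years for b) "Time to resumption of hormone therapy", c) "Time to initiation of any subsequent treatment", d) toxicity, e) "Site of relapse: within the irradiated field or at distant (non-irradiated) sites" and f) overall survival. Row d) also contains "late toxicity assessed at 2 years", so it carries two horizons.

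Section F (analysis of survival endpoints) censors patients without the event at the date last seen, and names Kaplan-Meier for progression-free and overall survival.

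**The concern.** Read literally, the table removes progression-free patients from scheduled observation at year 2 and keeps only those who have progressed. Kaplan-Meier assumes that censored patients have the same later risk as those who stay under observation. Here the patients who stay would be those with the worse prognosis, so 5-year survival would come out too low whenever death is more frequent after progression.

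The other 5-year endpoints are exposed in the same way. Hormone therapy resumption matters most, because the study background gives a longer interval between courses as a potential benefit; its 5-year estimate would rest on progressors alone. Relapses after year 2 would have no scheduled visit to detect them, so the in-field versus distant comparison would mainly describe early relapses. In addition, a patient whose progression is detected by month 18 has no scheduled late-toxicity assessment at 2 years.

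**Working it through.** **1. The plan's own figures.** Calendar: inclusion 24 months, treatment 6 months, follow-up 10 years, so 2 + 0.5 + 10 = 12.5 years, as stated. The sum works only if the 10 years apply to the last patient enrolled. Primary rule (section F): success at 39 or more of 63 gives exact binomial tails P(X ≥ 39 | 0.5) = 0.0385 and P(X ≥ 39 | 0.7) = 0.9356, against 3.85% and 93.5% stated. This rule is read at 24 months, inside the scheduled visits, so nothing below touches it.

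**2. Assumptions.** From section F: 2-year relapse-free survival p = 0.7 (alternative) or 0.5 (null), and 70 patients recruited. Assumed, because the documents give no hazards: exponential times, progression hazard h = −ln(p)/2 (0.1783 or 0.3466 per year), death hazard m0 = 0.01 before progression and m1 = 0.01, 0.02, 0.05 or 0.10 after it, no other loss, and the table followed literally.

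**3. Patients leaving scheduled observation at year 2.** p × e^(−0.02) = 0.686 or 0.490. Times 70, this is 48 or 34 patients; times the 63 evaluable, 43 or 31.

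**4. Overall survival at 5 years.**

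- True: OS(t) = e^(−(h+m0)t) + [h/(h+m0−m1)] × [e^(−m1·t) − e^(−(h+m0)t)].
- Table-based: after year 2 only progressors are at risk, so Kaplan-Meier tends to OS(2) × e^(−3·m1).

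Example, p = 0.7 and m1 = 0.10: h/(h+m0−m1) = 0.1783/0.0883 = 2.019. OS(2) = 0.6861 + 2.019 × (0.8187 − 0.6861) = 0.954. Table-based: 0.954 × 0.741 = 0.707. True: 0.3900 + 2.019 × (0.6065 − 0.3900) = 0.827.

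| Death hazard after progression | p = 0.7: true / table-based / gap | p = 0.5: true / table-based / gap |
|---|---|---|
| 1% per year | 95.1 / 95.1 / 0 | 95.1 / 95.1 / 0 |
| 2% | 93.5 / 92.0 / 1.5 | 92.7 / 91.8 / 0.9 |
| 5% | 89.1 / 83.3 / 5.8 | 85.8 / 82.5 / 3.3 |
| 10% | 82.7 / 70.7 / 12.1 | 76.0 / 69.2 / 6.8 |

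Values are percentages; gaps are points, taken before rounding. Simulations of these scenarios agree within simulation error. If a random half of progression-free patients is followed to 5 years anyway, the 12.1-point gap falls to 2.6; with 90% followed, to 0.4.

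**5. Hormone therapy resumption.** Further assumptions: Kaplan-Meier is used, resumption follows only progression detected at a 6-monthly visit, with an exponential delay of mean d years, and deaths are ignored. Table-based: (resumption-free at 2 years) × e^(−3/d). For p = 0.7 and d = 1: 0.856 × 0.0498 = 4%, against a true 52%. For d = 0.5, 1 and 2, true versus table-based is 47 v 0, 52 v 4 and 62 v 20% (p = 0.7), and 24 v 0, 29 v 4 and 42 v 19% (p = 0.5).

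**6. Relapses in years 2 to 5, constant hazard, deaths ignored.** 0.7 − 0.7^2.5 = 0.290 (20 of 70), which is 49% of the 0.590 relapsing by year 5. For p = 0.5: 0.5 − 0.5^2.5 = 0.323 (23 of 70), 39% of 0.823.

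**7. No scheduled 2-year late-toxicity assessment.** Constant hazard from time zero, progression detected by month 18: 1 − 0.7^0.75 = 0.235 (16 of 70) and 1 − 0.5^0.75 = 0.405 (28 of 70). With no relapse in the first 6 months and detection 6 months later: 1 − 0.7^(1/3) = 0.112 (8 of 70) and 1 − 0.5^(1/3) = 0.206 (14 of 70).

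**The case against.** The strongest reply is the 10-year line directly above the table. Since 12.5 years adds up only if that follow-up reaches the last patient enrolled, the sponsor evidently means to follow patients well past 5 years, and the table may simply not itemise those visits. This stands. A reader might infer that the plan deliberately stops observing progression-free patients at year 2, so that its 5-year survival estimate is certain to be biased. The documents do not support that: they contradict one another, and the bias arises only if the table is what sites follow. The 10-year line does not settle the matter either, because it names no visits or assessments.

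The public text may also be incomplete: the study diagram is not shown, and section F cites a section 8.5.1 that is not there. No visible text says whether vital status is collected outside the visits. If it is, the survival bias goes, but vital status alone would not supply treatment resumption or site of relapse.

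The larger figures need several assumptions at once. The 12-point gap takes a tenfold rise in the death hazard and no late contact with any progression-free patient. At 2% per year the gap is 1.5 points, small beside a simulated sampling standard deviation of about 5.8 points with 63 patients. The hormone therapy figures assume Kaplan-Meier, which section F names only for progression-free and overall survival. The higher late-toxicity counts ignore the 6 months of hormone therapy and the need for successive PSA rises. Section F analyses the highest grade per patient, so earlier visits still count. Imaging for site of relapse already depends partly on centre practice.

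A reader might also set the 5-year quality-of-life label against the tests at 6 and 12 months. Those can coexist, and no error follows.

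**Conclusion.** The plan contradicts itself on follow-up after year 2. The visit table cannot deliver the 5-year evaluation times for progression-free patients, and it disagrees with the 10-year follow-up. That much needs no assumptions.

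The statistical consequence is conditional. If the table governs, the downward bias in 5-year overall survival runs from 0 to about 12 points at 70% two-year relapse-free survival and from 0 to about 7 at 50%, over assumed post-progression death hazards of 1 to 10% per year. It is nil with equal hazards or complete vital status. Hormone therapy resumption could be distorted far more if Kaplan-Meier is applied to it. Only secondary endpoints are affected. It should be fixed, but it does not threaten the trial's main conclusion.

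**What to change.** Make sections C and G agree.

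- **Preferred:** extend the progression-free column to at least 5 years, within the 10 already stated, for vital status, treatment resumption and relapse status, at an interval the sponsor chooses.
- **Alternative:** limit the evaluation times of these secondary endpoints to what the scheduled visits cover.
- **Late toxicity:** schedule its recording to 2 years regardless of progression, and reconcile the 2-year and 5-year horizons in row d).

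The change is to the wording of the table and the evaluation-time labels; sample size and decision rule stay as they are. The downside of the preferred route is more follow-up data to collect and enter. The alternative avoids that but gives up the 5-year results.
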